## 7.1. Description of neuropsychological tests

#### Overview

The eligibility evaluation battery is administered to prospective participants at the time of the eligibility evaluation visit. Two neuropsychological test batteries are used for participants who enroll in ADAPT. A cognitive assessment battery is administered to participants at cognitive assessment visits to monitor cognitive function over time. A separate dementia evaluation battery is administered to those participants who show features of questionable or probable dementia based on the cognitive assessment battery or on clinical judgment. The dementia evaluation battery is used as an aid in the identification and differential diagnosis of dementia.

#### Eligibility evaluation battery

The eligibility evaluation battery includes two paper-and-pencil cognitive tests and one questionnaire administered to the participant's collateral respondent. A trained and certified psychometrician administers each of the tests according to the guidelines provided in the Eligibility Evaluation Battery and the ADAPT Neuropsychology Manual.

#### **Cognitive tests**

- Modified Mini-Mental State Examination Epidemiological (3MS-E): The measurement of global cognitive function, including orientation, language, verbal recall, recognition, long-term memory, praxis, and constructional ability, relies mainly on an adaption of the 100-point 3MS-E. The original test or one of the two equivalent alternate versions developed for the Cache County Study on Memory and Aging is used.
- Hopkins Verbal Learning Test Revised (HVLT-R): One of the six equivalent alternate forms of the HVLT-R^60 is used to measure verbal learning and delayed recall. In this test, a list of twelve words four from each of three semantic categories is ready to participants. Three learning trials are followed, after 20 to 25 minutes, by a delayed recall trial.

#### **Collateral respondent questionnaire**

• Dementia Severity Rating Scale (DSRS): The informant version of the DSRS is administered to the collateral respondent to assess cognitive and functional impairment.

### Cognitive assessment battery

The cognitive assessment battery includes six paper-and-pencil cognitive tests and two self-rating questionnaires administered to the participant, as well as one questionnaire administered to the participant's collateral respondent. A trained and certified psychometrician administers each of the tests according to the guidelines provided in the ADAPT Neuropsychology Manual.

# **Cognitive tests**

- *Modified Mini-Mental State Examination Epidemiological (3MS-E)*: The measurement of global cognitive function, including orientation, language, verbal recall, recognition, long-term memory, praxis, and constructional ability, relies mainly on an adaptation of the 100-point 3MS. The original test or one of two equivalent alternate versions developed for the Cache County Study on Memory in Aging is used.
- *Digit Span*: The Wechsler Adult Intelligence Scale Revised Digit Span subtest is used to assess auditory attention and working memory. Both forward and backward span is assessed. Both tests consist of six pairs of number sequences that the psychometrician reads aloud one at a time. After each sequence is read, the participant must repeat the digits back in the same (forward) or reverse (backward) order.
- Generative Verbal Fluency: This test measures verbal production, semantic memory, and language. Participants are asked to name as many supermarket items as possible in one minute.
- Narratives from the Rivermead Behavioral Memory Test: One of the four equivalent alternate versions of the Narratives from the Rivermead Behavioral Memory Test is used to assess immediate and delayed verbal memory. A brief passage is read to the participant. Immediately following auditory presentation of the passage, the participant is asked to recall the story. A final delayed recall trial is administered 15-20 minutes later.
- Hopkins Verbal Learning Test Revised (HVLT-R): One of the six equivalent alternate forms of the HVLT-R^60 is used to measure verbal learning, recognition, and delayed recall. In this test, a list of twelve words—four from each of three semantic categories—is read to participants. Three learning trials are followed, after 20 to 25 minutes, by a delayed recall trial and then a yes/no recognition trial.

• Brief Visuospatial Memory Test - Revised (BVMT-R): One of the six equivalent alternate forms of the BVMT-R^64 is used to assess immediate and delayed nonverbal memory. The participant is presented with a card depicting six simple designs. After the designs are studied for a brief time period, the card is removed and the participant must immediately draw the designs from memory. Approximately 10-15 minutes after initial presentation, the participant is asked to draw the designs again. Immediately thereafter, a yes/no recognition trial is administered.

## **Self-administered questionnaires**

- *Self-Rating of Memory Functions*: To determine the participant's perception of memory and other cognitive changes, the 18-item Self-Rating of Memory Functions is administered. Participants respond to 18 items that ask them to rate changes over the past year using a 9-point Likert scale. Each item asks participants to judge their memory now compared to an earlier time period.
- Geriatric Depression Scale (GDS): To determine the participant's perception of depression, the 30-item GDS is administered.

#### Collateral respondent questionnaire

• *Dementia Severity Rating Scale (DSRS)*: The informant version of the DSRS is administered to the collateral respondent to assess cognitive and functional impairment.

#### **Dementia evaluation battery**

The dementia evaluation battery includes eleven paper-and-pencil cognitive tests and one memory rating scale administered to the participant, and three questionnaires administered to the collateral respondent. A trained and certified psychometrician will administer the tests according to the standardized guidelines provided in the ADAPT Neuropsychology Manual.

#### **Cognitive tests**

• *The CERAD Battery*: The battery developed by the Consortium to Establish a Registry for Alzheimer's Disease is administered. This battery includes the following tests:

*Generative Verbal Fluency*: This test measures verbal production, semantic memory, and language. Participants are asked to name as many animals as possible in one minute.

*Short Boston Naming Test*: A modification of the Boston Naming Test measures expressive language. Participants are asked to name 15 line drawings of varying difficulty.

*Mini-Mental State Examination (MMSE)*: This 30-item brief cognitive test measures orientation, immediate and delayed memory, concentration, language and praxis.

Word List Memory: This test measures verbal learning and the ability to remember newly learned information. A list of ten printed words is read to the participant who is then asked to recall as many words as possible. This is followed by two additional learning trials. To assess delayed recall, participants are asked to recall the ten previously presented words after a period of approximately 5 minutes has elapsed from initial presentation. To measure recognition, the ten target words are presented among ten distracters.

Constructional Praxis: To assess visuomotor ability, four line drawings of varying complexity are presented to the participant for copying. After a time delay, participants are asked to recall and draw the four designs.

- *Trail Making Test*: This timed test is used to measure attention, executive function, and visuomotor tracking. To complete Part A, the participant must draw lines to connect consecutively numbered circles. To complete Part B, they must connect consecutively numbered and lettered circles by alternating between the two sequences.
- Logical Memory: The Logical Memory I subscale of the Wechsler Memory Scale –
  Revised is used to assess immediate verbal memory. Two brief passages are read to the
  participant. Immediately following auditory presentation of each passage, the participant
  is asked to recall the story. The Logical Memory II subscale of the Wechsler Memory
  Scale Revised is used to assess delayed verbal memory. Approximately 30 minutes
  after completion of Logical Memory I, participants are once again asked to recall the two
  verbal passages.
- Benton Visual Retention Test (BVRT): One of three equivalent alternate forms of the BVRT is used to assess immediate visual/nonverbal memory. In this test, a design is placed in front of the participant. After the drawing is studied for a brief time period, it is removed and the participant must immediately draw it from memory. Each form of the BVRT includes ten different designs of varying difficulty.
- Controlled Oral Word Association Test (COWA): Fluency of speech is assessed using COWA. The number of words produced within 1 minute for three specified letters of the alphabet is recorded.

- Symbol Digit Modalities Test (SDMT): To measure complex scanning and visual tracking, the SDMT is used. In this timed test, the digits 1 through 9 are associated with a nonsense symbol. When presented with a row of symbols and blank spaces, the participant must write the number in the space that corresponds to each symbol.
- Shipley Vocabulary: The vocabulary subtest of the Shipley Institute of Living Scale is used to assess premorbid verbal ability or verbal IQ. The participant is asked to circle one of four words that most closely matches the meaning of a target word. The 40-item list is progressively more difficult.

#### **Memory scale**

• *Self-Rating of Memory Functions*: To determine the participant's perception of memory and other cognitive changes, the 18-item Self-Rating of Memory Functions is administered. Participants respond to 18 items that ask them to rate changes over the past year using a 9-point Likert scale. Each item asks participants to judge their memory now compared to an earlier time period.

#### Collateral respondent questionnaires

- *Dementia Severity Rating Scale (DSRS)*: The informant version of the DSRS is administered to the collateral respondent to assess cognitive and functional impairment.
- Dementia Questionnaire (DQ-cr): The clinical revision of the Dementia Questionnaire is administered to the collateral respondent to assess memory and activities of daily living. The DQ-cr is a 50-item semistructured inventory of dementia symptoms and medical history developed to aid in the differential diagnosis of dementia.
- *Neuropsychiatric Inventory (NPI)*: The NPI is a structured informant interview to assess behavioral and psychiatric symptoms. Using a series of graded questions, the informant is asked whether the participant has experienced each of 10 domains in the past month: delusions, hallucinations, agitation, depression, anxiety, elation, apathy, disinhibition, irritability, and aberrant motor behavior

## 7.2. Diagnosis of dementia

The results of each dementia evaluation visit will be reviewed at a conference of the site clinical team. Ordinarily, this team will comprise the field site director, the associate field site director, the examining study physician and nurse, and the site neuropsychologist. The clinical team will record a judgment regarding the presence of dementia, as defined by DSM-IV criteria. At this initial field site conference, one of the following three impressions will be reached:

### • Participant is thought to be cognitively normal

- Participant should remain on study treatment
- Participant should return to regular followup and annual cognitive assessment

# • Participant meets the Petersen criteria for mild cognitive impairment (MCI) or appears to have a clinical syndrome consistent with prodromal AD

- Participant should remain on study treatment
- Participant should return to regular followup and annual cognitive assessment
- Field site staff should monitor for evidence of further decline that may warrant referral for a repeat DEV

#### • Participant is thought to have a dementia syndrome

- Study personnel should refer participant for laboratory evaluation of thyroid stimulating hormone, rapid plasma reagin (for syphilis), and vitamin B12 and folate, as well as for standard clinical MRI (or, alternatively, CT scanning, if MRI is contraindicated); details regarding referral for laboratory tests and imaging are specified in the ADAPT Handbook
- Upon completion of laboratory tests and imaging, a second field site conference should be scheduled to review the results and to record clinical impressions on the differential diagnosis of the presumed dementia syndrome; the field site clinical team should refer to section 9.2 of the ADAPT Handbook for specific instructions on diagnostic criteria
- For the purposes of the followup procedures described in section 7.3, a participant should be considered to have a diagnosis of dementia only when that diagnosis is considered by the field site clinical team to be reasonably certain and irreversible.

## 7.3. Followup of participants diagnosed with dementia

When the field site clinical team has reached a reasonably certain diagnosis of irreversible dementia, they should direct the participant to stop study treatment and should refer him or her to a dementia clinic for care. For as long as possible, however, the participant should return for regular ADAPT followup and annual cognitive assessment. When individuals with dementia are considered unable to make decisions about their continued participation in the trial, consent for such participation must be obtained from a responsible third party, along with assent from the participant if this is meaningful.

## 7.4. Incidence of Alzheimer's disease

For analyses of the incidence of AD, participants with a diagnosis of dementia will be considered to have the event when the field site team has reached a differential diagnosis of possible or probable AD using NINCDS/ADRDA criteria. On occasion, at a subsequent visit participants with a prior diagnosis of possible or, rarely, probable AD will show a clinically unexpected change that calls the diagnosis into question. In such instances the site medical director or other study physician will schedule a new dementia evaluation visit, with followup laboratory testing if clinically indicated. However, even if a participant's diagnosis is thought to have changed, for the purpose of

ADAPT and its outcome measures, the database diagnosis will not be revised and the participant remain off study medication. Such cases should receive particular attention by the Diagnostic Review Committee.

# 7.5. Diagnostic Review Committee

The Diagnostic Review Committee will comprise the field site directors or associate directors, the Study Chair, and at least one senior neuropsychologist. The Committee will meet approximately every 6 months to review all newly identified presumed and all substantially revised cases of dementia. Material to be reviewed include the results of the dementia evaluation battery, laboratory testing, and neuroimaging. The purpose of the Committee reviews is to promote the homogeneity and standardization of diagnoses across the ADAPT field sites.

# 8. Analysis plan

### 8.1. General principles

General principles for analysis include the following:

- The primary analysis will be performed according to participants' original treatment assignment (intention to treat), regardless of administered treatment
- All participants, including those who are found to be ineligible after randomization or those who withdraw from the study, will be counted in their assigned treatment group once that treatment assignment has been revealed
- All events following randomization will be counted
- Subjects with missing measures at a particular time will be excluded from analyses that
  require those measures but will not be excluded from other analyses for which data are
  available

Analyses will be done to look for differences in outcome between each of the groups receiving active treatment and the placebo-treated group. Results of analyses will be presented unadjusted and adjusted. Covariates to be used for adjusting treatment group effects will include field site (also a stratification variable), age at entry (a stratification variable in the form of age categories), APOE genotype, gender, and other prospective baseline risk factors chosen with clinical judgment and/or variable selection procedures such as forward selection. Exploratory analyses will be performed in which post randomization data, such as adherence to the assigned treatment regimen or treatment received, will be taken into account. In addition, treatment effects will be examined across various subgroups.

Formal adjustment procedures will not be used for p-values resulting from the comparisons of each of the active treatment groups with the placebo group or from multiple comparisons made during interim monitoring. In the comparisons of the active treatments to placebo, the two treatment comparisons (naproxen sodium vs. placebo and celecoxib vs. placebo) are viewed as tests of separate experimental hypotheses. With respect to interim monitoring, it is to be expected that numerous comparisons of treatment efficacy and safety must be performed over the course of a clinical trial. Rather than to adjust p-values for multiple comparisons, p-values will be interpreted as descriptive statistics of the evidence, and not as absolute indicators for a positive or negative result.

#### 8.2. Analysis of design variable

The analysis of incidence of AD will be drawn from multivariate survival analytic models, which account for censoring and allow for adjustment for multiple covariates. In the principal analysis, time-to-event methods will be used to model the effect of assigned treatment on the development of AD. (Secondary analyses of the treatment effects will include adjustments for adherence to the assigned study treatment.)

The survival analysis models will control for age at entry and other prospective baseline risk factors. Because age is a strong determinate of risk for AD, and because the association of age and AD is not linear, various models that adjust for age may be created. At the least, age will be included in the same categories used for stratification at randomization (ages 70-74, 75-79, and 80+). Finer categories may be used if there is evidence of residual confounding from imbalance in the age distribution among the treatment groups. However, it is expected that with stratification and a planned sample size of 2,625, such confounding is unlikely. Age-by-treatment interactions also will be investigated using the above stratification categories.

Other covariates to be included in the survival analysis models will include a core set of established predictors of AD incidence, as determined from epidemiological studies. Such factors include *APOE* genotype, education, gender, use of estrogen, use of anti-oxidants, and a history of head injury (family history of dementia is irrelevant here, as it is a criterion for enrollment). Again, it is expected that these variables will be balanced among treatment groups at enrollment, but analyses will be done to assess whether observed treatment effects are independent of them. Other baseline variables may be included if they are unbalanced across treatment groups.

Proportional hazards models may fail to adequately describe the treatment effects. For example, such effects may become apparent only after a threshold amount of time in treatment with naproxen sodium or celecoxib. In other words, the treatment effect may depend on the duration of followup. Accordingly, interactions between the treatment effect and followup time, using time-dependent covariates for such interactions with treatment, may be considered.

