### 3.2. Sample size and power

Sample size is calculated to allow detection of at least a 30% reduction in the incidence of AD. Such a reduction will be detectable with 80% power and a two-sided  $\alpha = 0.05$  over 7 years of followup. Calculations were based on the log-rank statistic, under the following additional parameter assumptions:

- **Incidence rate**: It is estimated that the incidence rate of this population, "enriched" for family history of Alzheimer-like dementia, will be 2.5% in the first year, and that there will be a 10% proportional increase in each of the subsequent years (2.75% in the second year, 3.03% in the third year, and so on).
- Mortality rate: The mortality rates projected for the study population represent a base mortality rate in the first year of 4%, increasing by a factor of 8.5% in the subsequent years (4.34% in the second year, 4.71% in the third year, and so on).
- Losses to followup or refusals of further follow-up: A loss of 5% of participants each year is assumed for reasons such as participant relocation or refusal to continue in the study.
- Adherence to assigned treatment: The power of the study is affected 1) when participants assigned to active treatment stop taking the study medication and do not thereafter take an NSAID on a regular basis and 2) when participants assigned to placebo become regular NSAID users. The first situation is projected to occur in 15% of participants assigned to active medication during the first year and in an additional 5% for each of the remaining years. The second scenario is thought to be less probable (participants will be more likely to become intermittent, rather than regular, users of NSAIDs). It is therefore estimated that 2.5% of participants assigned to placebo will become regular NSAID users in each year.

Under the assumptions outlined above, the required sample size is approximately 2,625.

2. Objectives

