### 3.3. Eligibility criteria

### **Inclusion criteria**

- Age 70 years or older at time of the eligibility evaluation visit
- Family history of one or more first-degree relatives with Alzheimer-like dementia
- A collateral respondent available to provide information on the cognitive status of the participant and to assist with monitoring of trial medications, if needed
- Sufficient fluency in written and spoken English to participate in study visits and neuropsychological testing
- Willingness to limit use of the following for the duration of the study:
  - vitamin E (at doses > 600 IU per day)
  - non-aspirin NSAIDs or aspirin (> 81 mg per day)
  - histamine H2 receptor antagonists
  - Ginkgo biloba extracts
- Ability and intention to participate in regular study visits, in the opinion of the study physician
- · Provision of informed consent

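### Section 8.2 commits only to three age bands and ties finer coding to imbalance, although a pre-specified flexible age term would be at least as efficient at almost no cost

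*Protocol*

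**What the plan says.** Protocol section 8.2 gives its premise first: "Because age is a strong determinate of risk for AD". It goes on: "because the association of age and AD is not linear, various models that adjust for age may be created". The minimum coding follows: "At the least, age will be included in the same categories used for stratification at randomization (ages 70-74, 75-79, and 80" and over. Finer coding is conditional: "Finer categories may be used if there is evidence of residual confounding from imbalance in the age distribution among the treatment groups". The same paragraph then says such confounding is unlikely, given the stratification and the planned 2,625 participants. For effect modification it says: "Age-by-treatment interactions also will be investigated using the above stratification categories".

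Section 8.1 also lists age at entry as an adjustment covariate, describes it as a stratification variable in category form, and promises both unadjusted and adjusted results. Neither section names a continuous or spline term for age. Section 3.2 bases the sample size on the log-rank statistic.

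**The concern.** The protocol gives the right reason for modelling age well, namely that it is strongly and non-linearly related to AD, and then makes better modelling depend on something else. Imbalance is a reason to adjust against bias. It is not the reason to use a strong prognostic factor in a hazard model. When a strong predictor is coded coarsely, the variation left inside each band pulls the estimated log hazard ratio toward zero and lowers the test statistic, even with perfectly balanced arms. The 80+ band is the widest and has no upper limit.

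Because the only stated trigger is one the protocol does not expect to occur, the plan followed as written will probably stay at three bands. If the trigger did occur, the age coding of the principal model would be chosen after looking at the data. At stake is a little power in each active-versus-placebo comparison, forgone although age is known for every participant.

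**Working it through.** **Inputs from the protocol.** Section 3.2: 30% reduction (hazard ratio 0.70), two-sided alpha 0.05, 80% power, 7 years; AD incidence 2.5% in year 1, growing by a factor of 1.10 per year; mortality 4%, growing by 1.085; loss 5% per year. Section 3.4: allocation 1:1:1.5, so 750 active and 1,125 placebo per comparison, with active share 750/1,875 = 0.40.

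**Assumed, because the protocol gives no figure.** The age distribution (right-skewed from 70, mean 74 to 77) and the hazard ratio per 5 years of age (1.28 to 2.46). Section 3.2 states "there will be a 10% proportional increase in each of the subsequent years", but that is growth in cohort incidence over follow-up, not a slope across entry ages. A 10% gradient per year of age is therefore borrowed as a plausible low value.

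**Step 1: the planned figure.** Events needed = (1.960 + 0.842)² / (0.40 × 0.60 × (ln 0.70)²) = 7.849 / 0.03053 = 257.1, so 258. Running the yearly rates forward month by month, as hazards −ln(1 − rate) with AD, death and loss competing, gives about 170 placebo and 82 active events, 252 in all; other time-step conventions give up to 256. Power at 252 events is Φ(√(252 × 0.24) × 0.3567 − 1.960) = Φ(0.814) = 0.79, and at 256 events it is 0.80. The implied N is 2,625 × 258/256 = 2,646 to 2,625 × 258/252 = 2,688. The planned 2,625 is reproduced when the 30% is read as the effect in the groups as randomized. Whether the stated drop-out and drop-in rates dilute it is a separate question that this point does not rely on.

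**Step 2: bands against continuous age.** Cox models were simulated with 1,500 trials per scenario, n = 1,875, hazard ratio 0.70 and allocation balanced within the three bands. Exit rates followed section 3.2 and did not depend on age. Raw power is Φ(mean Z − 1.960). To put scenarios on one scale, let r = (mean Z, bands) / (mean Z, continuous). Then r² is the share of information the bands keep, and Φ(2.802 r − 1.960) is the power with bands when continuous age would give 80%.

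| Mean age | HR per 5 y | Mean events | Raw power, bands / continuous | r | r² | Bands, if continuous = 80% | Unadjusted, if continuous = 80% |
|---|---|---|---|---|---|---|---|
| 75 | 1.28 | 250 | 0.756 / 0.756 | 1.000 | 1.00 | 80.0% | 79.6% |
| 75 | 1.65 | 243 | 0.743 / 0.749 | 0.993 | 0.99 | 79.4% | 77.7% |
| 74 | 2.01 | 238 | 0.725 / 0.736 | 0.987 | 0.97 | 79.0% | 76.7% |
| 75 | 2.01 | 230 | 0.707 / 0.727 | 0.977 | 0.95 | 78.1% | 74.5% |
| 77 | 2.01 | 220 | 0.632 / 0.682 | 0.944 | 0.89 | 75.3% | 70.8% |
| 75 | 2.46 | 209 | 0.648 / 0.690 | 0.953 | 0.91 | 76.1% | 70.2% |
| 75 | 2.01, flat after 85 | 241 | 0.743 / 0.744 | 0.999 | 1.00 | 79.9% | 77.3% |

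Worked row (mean age 75, 2.01): Z for bands = 0.545 + 1.960 = 2.505; Z for continuous = 0.604 + 1.960 = 2.564; r = 0.977; Φ(2.802 × 0.977 − 1.960) = Φ(0.777) = 0.781.

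The rows with 1.65 and 2.01 correspond to a gradient of about 10% per year of age and to a doubling every 5 years. Across them the bands lose 0.1 to 4.7 points. Adding a quadratic age term left power within 0.002 of the linear term in every row.

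**Step 3: cross-checks.** A separate simulation with exponential ages (mean 74 to 76, 400 runs per scenario) gave 1-4% more information with continuous age at 10% per year of age, and 5-11% at a doubling every 5 years. For example, (2.46/2.33)² = 1.11. A further simulation that fitted a 3-knot restricted cubic spline gave about 0-7% more information than the bands, or 0 to about 3 power points. The spline gained nothing under a plateau at 85 and was never materially worse.

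**The case against.** The strongest reply is that the bands are a floor, not the fixed coding. Section 8.2 says at the least, and it allows other age models because the association is not linear. A reader might infer that the plan bars continuous age; it does not. This stands, and it limits the point to what the protocol commits to and to the trigger it names. The optional wording does not repair that trigger.

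A reader might also infer that the trial falls short of its 80% power. The documents do not support this. Planning used the log-rank statistic without covariates, and in every scenario above the bands do better than no adjustment, by 0.4 to 6 points.

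Third, the larger gains depend on assumed gradients and age distributions. Most of the simulations also generate log-linear age, which favours a continuous term; under a plateau the gain vanishes. This stands and is why the size is given as a range starting at zero. Section 8.1 also treats p-values as descriptive, so one or two power points would rarely change a conclusion.

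Two extensions are tempting. Section 8.2 sets family history aside: "family history of dementia is irrelevant here, as it is a criterion for enrollment". The criterion reads: "Family history of one or more first-degree relatives with Alzheimer-like dementia". The number of affected relatives can therefore still vary. But the protocol does not show that the count is recorded (section 5.3 says only that family history is obtained at screening), and no gain was computed, so adding it as a covariate is not requested. Likewise, no power loss was computed for the age-by-treatment analysis, and none is claimed.

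**Conclusion.** The point holds as a minor matter of efficiency and pre-specification. Section 8.2 commits only to a three-band age adjustment and makes finer categories depend on imbalance, when the reason to model age well is the prognostic strength the protocol itself states. A pre-specified flexible continuous term is at least as efficient. For gradients between 10% per year of age and a doubling every 5 years, and mean entry ages of about 74 to 77, it gains about 0 to 5 power points, mostly 0 to 2, and about none if risk plateaus near 85. Both the gradient and the age distribution are assumptions. The planned power is not undermined, and no bias or type I error problem follows from the bands.

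**What to change.** In section 8.2, replace the sentence that makes finer categories depend on imbalance with a statement that age at entry enters the principal AD model as a restricted cubic spline with 3-4 knots, whatever the observed balance. A spline rather than a single linear term answers the protocol's own remark on non-linearity. Keep the three bands for randomization and for tabulation. Optionally, examine the age-by-treatment interaction with continuous age as well.

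The cost is a wording change, with no new data and no more participants. The spline uses 2 to 3 degrees of freedom against 2 for the bands. Even a few extra would be negligible at about 250 events per comparison.
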